## 8. Data for a CONSORT diagram and “study realization”

This data are analyzed exclusively for the final statistical analysis report. Data are reported for all patients in the complete ITT analysis set as well as separately for the BioMonitor and the control group and for the complete PP analysis set as well as for the BioMonitor and the control group, respectively.

### 8.1. Enrollment

- Number of patients
- Number of patients per site
- Date of First-Patient-In
- Date of Last-Patient-In

### 8.2. Termination

- Date of First-Patient-Out
- Date of Last-Patient-Out
- 

Data file: Identifier patient_display id_full	Notes	Variable name	Variable label	Variable level	Nominal values
study_termination	descriptive	regular_yn	Regular study termination	nominal	Yes No
study_termination	Descriptive for regular_yn = No	reason_multi	Please indicate the reason for early study termination	nominal	Patient death Withdrawal of patient consent Investigator initiated drop-out Loss to follow-up Early discovery of a violation of inclusion or exclusion criteria Heart transplantation Other

Data file: Identifier patient_display_id_full	Notes	Variable name	Variable label	Variable level	Nominal values
enrollment	Case listings for regular_yn = No	ic_date	Date of informed consent	date	n.a.
discharge		discharge_date	Date of discharge from index hospitalization		
study_termination		term_date	Date of study termination		
study_termination		reason_multi	... reason for early study termination	nominal	

Data file: Identifier patient_display _id_full	Notes	Variable name	Variable label	Variable level	Nominal values
study_termination	descriptive data including cumulative duration	days_dis_term_ITT_SAR 	Days from effective randomization for ITT analysis to termination	metric	n.a.
study_termination	descriptive data including cumulative duration	days_dis_term_PP_SAR 	Days from effective randomization for PP analysis to termination	metric	n.a.

## 9. Baseline Data

### 9.1. Analysis set

These data are analyzed exclusively for the final statistical analysis report. Data are reported for all patients in the complete ITT analysis set as well as separately for the BioMonitor and the control group and for the complete PP analysis set as well as for the BioMonitor and the control group, respectively.

### 9.2. Variables

#### Enrollment

Data file: Identifier patient_display_id_full	Notes	Variable name	Variable label	Variable level	Nominal values
baseline	descr.	gender_fm	Gender	nominal	Male / Female
baseline					
enrollment	descr.	ami_lma	Left main artery	nominal	True / False
enrollment	descr.	ami_lad	Left anterior descending artery (LAD)	nominal	True / False
enrollment	descr.	ami_cx	Circumflex artery (CX)	nominal	True / False
enrollment	descr.	ami_rca	Right coronary artery (RCA)	nominal	True / False
enrollment	descr.	amitreat_pr	Percutaneous revascularization	nominal	True / False
enrollment	descr.	amitreat_t	Thrombolysis	nominal	True / False
enrollment	descr.	amitreat_0	NEW: Other kind of MI treatment	nominal	True / False
enrollment	descr.	amikind_multi	Kind of MI	nominal	STEMI / NSTEMI
enrollment	descr.	amifirst_yn	First occurrence of MI	nominal	Yes / No
enrollment	descr.	ami_no	Number of previous MI	metric	n.a.

#### Baseline

Data file: Identifier patient_display_id_full	Notes	Variable name	Variable label	Variable level	Nominal values
baseline	descr.				
baseline	descr.	hidden_age	Age at enrollment	Scale	n.a.
baseline	descr.	weight_kg	Weight [kg]	scale	n.a.
baseline	descr.	height_cm	Height [cm]	scale	n.a.
baseline	descr.	bmi	BMI [kg/m2]	scale	n.a.
baseline	descr.	bsa	BSA (Mosteller) [m2]	scale	n.a.
baseline	no report	lvef_percent	NEW: LVEF after initial AMI treatment [%]	scale	n.a.
baseline	no report	lvef_percent_amend1	NEW: LVEF measurement, performed within 6 months before enrollment [%]	scale	n.a.
data_SAR	descr.	lvef_SAR 	LVEF (before amendment or -if missing-after amendment) [%]	scale	n.a.
baseline	descr.	lav_ml	Left atrial volume [ml]	scale	n.a.
baseline	descr.	ldv_ml	Left ventricular diastolic volume [ml]	scale	n.a.
baseline	descr.	ldvbsa_mlm2	LVDV/BSA [ml/m2]	scale	n.a.
baseline	descr.	lsv_ml	Left ventricular systolic volume [ml]	scale	n.a.
baseline	descr.	lsvbsa_mlm2	LVSV/BSA [ml/m2]	scale	n.a.

Data file: Identifier	Notes	Variable name	Variable label	Variable level	Nominal values
patient_display_id_full					
baseline	descriptive	Gender_fm	Gender	nominal	Female / Male
baseline	descriptive	chf_yn	NEW: Congestive Heart Failure	nominal	Yes / No
baseline	descriptive	chfnhya_multi	NYHA class	nominal	I / II / III / IV
baseline	descriptive	nyha_SAR 	NYHA class	ordinal	1 / 2 / 3 / 4
baseline	descriptive	str_yn	Stroke	nominal	Yes / No
baseline	descriptive	tia_yn	Transient ischemic attack	nominal	Yes / No
baseline	descriptive	ste_yn	Systemic thromboembolic event	nominal	Yes / No
baseline	descriptive	hyp_yn	Hypertension	nominal	Yes / No
baseline	descriptive	pad_yn	Peripheral artery disease	nominal	Yes / No
baseline	descriptive	dia_yn	Diabetes mellitus	nominal	Yes / No
baseline	descriptive	vhd_multi	Valvular heart disease	nominal	Yes / No / Not known
baseline	with	mca_multi	Myocarditis	nominal	Yes / No / Not known
baseline	"Not known "	ren_multi	Renal disease	nominal	Yes / No / Not known
baseline	to be	thy_multi	Thyroid dysfunction	nominal	Yes / No / Not known
baseline	analyzed	cop_multi	COPD	nominal	Yes / No / Not known
baseline	as missing	hep_multi	Hepatic disease	nominal	Yes / No / Not known
baseline	data	sle_multi	Sleep apnea	nominal	Yes / No / Not known
baseline	descriptive	chads2_SAR 	CHADS2 Score	ordinal	0 / 1 / 2 / 3 / 4 / 5 / 6
data_SAR	descriptive	chads2_SAR 	CHADS2 Score (SAR)	ordinal	0 / 1 / 2 / 3 / 4 / 5 / 6
baseline	descriptive	cha2ds2vasc 	CHA2DS2-VASc-Score	ordinal	0 / 1 / 2 / 3 / 4 / 5 / 6 / 7 / 8 / 9
baseline	descriptive	cha2ds2vasc_SAR 	CHA2DS2-VASc-Score (SAR)	ordinal	0 / 1 / 2 / 3 / 4 / 5 / 6 / 7 / 8 / 9

Lab parameter

Data file: Identifier patient_display_id_full	Notes	Variable name	Variable label	Variable level	Nominal values
discharge	no report	date_created	Date created	date	n.a.
discharge	descriptive	lab1	Potassium [mmol/l]	scale	n.a.
discharge	descriptive	lab2	Sodium [mmol/l]	scale	n.a.
discharge	no report	lab3	Troponine	scale	n.a.
discharge	no report	lab3_multi	Troponine: Specification	nominal	Troponin C (Tn-C) ng/ml Troponin I (cTnI) ng/ml Troponin T (cTnT) Åµg/l
data_SAR	descriptive	lab3c_SAR 	Troponine C [ng/ml]	scale	n.a.
data_SAR	descriptive	lab3i_SAR 	Troponine I [ng/ml]	scale	n.a.
data_SAR	descriptive	lab3t_SAR 	Troponine T [mue_g/l]	scale	n.a.
discharge	descriptive	lab4	eGFR [ml/min]	scale	n.a.
discharge	no report	lab5	NEW: Haemoglobin	scale	n.a.
discharge	no report	lab5_multi	Please specify		mmol/l g/dl
data_SAR	descriptive	lab5_SAR 	Haemoglobin [mmol/l]	scale	mmol/l

Medication

Data file: Identifier patient_display_id_full	Notes	Variable name	Variable label	Variable level	Nominal values
discharge	descriptive	concm01 - concm11	Cardiovascular medication	nominal	Yes/ No
discharge	descriptive	nconcm1- noconcm4	Non-cardiovascular medication	nominal	Yes/ No
discharge	case listing for concm09 = True OR concm11 = True	concm0911_spec	Please specify (Anticoagulation treatment Other)	text	n.a.

### 9.3. Treatment of Missing and Spurious Data

Missing data are not imputed.

Spurious data, which were not clarified by the query process before CDMS closure, are indicated. If appropriate, descriptive and inferential analyses are performed both with /without such data.

### 9.4. Exclusion of Particular Information

No data from the previous defined analysis set are excluded from the analysis except those defined in chapter 5.5, if applicable.

### 9.5. Descriptive Analyses

Descriptive data are presented via tables as specified in chapter 5.1.

### 9.6. Hypotheses & Statistical Tests

There are no pre-defined statistical hypotheses / tests for the baseline data in the CIP.

However, a potential imbalance between BioMonitor and control group with respect to the stratification variable amikind\_multi = STEMI/NSTEMI will be analyzed based on Fisher's exact test.

---

 Even if the randomization procedure will not sufficient and there will be an imbalance amikind\_multi = STEMI / NSTEMI, no bias is expected for the primary endpoint analysis based on the stratified logrank test.

## 10. Pre-processing EAEC data for the primary and secondary endpoints

Each event from the EAEC-adjudication data file is identified by a parent\_record\_id variable. There are at least three data lines per event containing the adjudication of the three board members. In case of deviating decisions of the board members for a specific variable, a 2-of-3 decision is used for further analyses. However, a final adjudication of the chair, which is identified by the variable eac\_complete\_chair = Yes, overrules the evaluations of the other EAEC Members. According to EAEC working procedure, there are at least 2 identical adjudications or a chair decision for each event.

In its initial adjudication, the EAEC classifies the uncorrected cause of the event with all available information including BioMonitor data. Next, for any possible endpoint, the most probably adjudication result without BioMonitor information is documented. The analyses of the endpoints will be based on this variables type\_of\_event\_ae2 and death\_prim\_cause2, which are in better accordance with the objective of the study. However, for the primary endpoint a safety analysis is also performed for the uncorrected variables type\_of\_event\_ae and death\_prim\_cause.

### CIP Chapter 8.3.1 Primary Endpoint

*The primary endpoint is the time from randomization (definition see section 8.2.1) to the first MACE during the clinical investigation. Patients without MACE are censored, i.e. the time from randomization until the earliest date of drop-out, study termination, or date of freezing the Clinical Data Management System database (in case of interim analyses) is considered. Patients who reach the primary endpoint will continue to be followed up until the formal termination of the study is announced (see section 8.1).*

*A major adverse cardiac event (MACE) comprises the following events:*

- *Cardiovascular death*
- *Worsening of the patient status due to heart failure, requiring acute unscheduled hospitalization or urgent visit*

*or acute unscheduled hospitalization due to adverse events (AE) of the following list:*

- *Arrhythmia*
- *Acute coronary syndrome*
- *Stroke*
- *Major bleeding*
- *Systemic embolism*

Heart transplantation (HTX) is also a component of "worsening of the patient status due to heart failure, requiring acute unscheduled hospitalization or urgent visit".

 The „uncorrected“ adjudication refers to the assumed true cause of the event after considering of all available information including that coming from the BioMonitor. Because the latter is not available in the control group, this information bias can distort the true treatment effect, and the primary analysis of the treatment effect is based on the adjudication that the EAEC gives und the assumption that no BioMonitor information was available. A detailed justification is given in the EAEC charter.

Data file: Identifier record_id	Notes	Variable name	Variable label	Variable level	Nominal values
eaec_ adjudication	No report	eaec_ complete_ chair	Is chair adjudication for this event applied and complete?	nominal	Yes No
eaec_ adjudication	No report	type_of_ event	Please specify type of event	nominal	Death without prior hospitalisation Heart transplantation Acute unscheduled hospitalisation or urgent HF visit Scheduled hospitalisation or Home Monitoring triggered No hospitalisation / no endpoint due to other reason
eaec_ adjudication	No report	type_of_ event_ae 	Primary cause of Unscheduled hospitalisation / urgent visit	nominal	Myocardial infarction Heart failure (urgent visit) Heart failure (hospitalisation) Arrhythmia Stroke Major bleeding Transient ischemic attack Systemic embolism other cardio-vascular non-cardiovascular Undetermined hospitalization or undetermined urgent visit
eaec_ adjudication	No report	death_ prim_cause	Primary cause of death	nominal	Myocardial infarction Heart failure Sudden cardiac death Stroke Cardiovascular hemorrhage Systemic embolism other cardio-vascular non-cardiovascular undetermined
eaec_ adjudication	No report	date1_ of_event	Date of event	date	n.a.
eaec_ adjudication	No report	date2_deat h	Date of death	date	n.a.
eaec_ adjudication	No report	death_ occured	Patient death during hospitalization / transplantation	nominal	Yes No

 Note new classification "Undetermined hospitalization or undetermined urgent visit"

Data file: Identifier record_id	Notes	Variable name	Variable label	Variable level	Nominal values
eaec_ adjudication	No report	contribution_ significant	The BioMonitor contributed significantly to the adjudication result, so that the result would most probably have been different without the information from the BioMonitor	nominal	Yes No
eaec_ adjudication	No report	type_of_ event_ae2	Primary cause of Unscheduled hospitalisation / urgent visit  The most probably adjudication result without BioMonitor information would have been	nominal	Myocardial infarction Heart failure (urgent visit) Heart failure (hospitalisation) Arrhythmia Stroke Major bleeding Transient ischemic attack Systemic embolism other cardio-vascular non-cardiovascular
eaec_ adjudication	No report	death_ prim_cause2	Primary cause of death  The most probably adjudication result without BioMonitor information would have been	nominal	Myocardial infarction Heart failure Sudden cardiac death Stroke Cardiovascular hemorrhage Systemic embolism other cardio-vascular non-cardiovascular undetermined
data_eaec_ adjudication_ SAR	No report	type_of_ event_ae_c 	Primary cause of Unscheduled hospitalisation / urgent visit (corrected data)	nominal	Myocardial infarction Heart failure (urgent visit) Heart failure (hospitalisation) Arrhythmia Stroke Major bleeding Transient ischemic attack Systemic embolism other cardio-vascular non-cardiovascular
data_eaec_ adjudication_ SAR	No report	death_ prim_cause_c 	Primary cause of death (corrected data)	nominal	Myocardial infarction Heart failure Sudden cardiac death Stroke Cardiovascular hemorrhage Systemic embolism other cardio-vascular non-cardiovascular undetermined

Data file: Identifier parent_record_id	Notes	Variable name	Variable label	Variable level	Nominal values
data_ep_SAR	No report	pep_c_2of3chair_SAR 	(Corrected) primary EP (based on a 2-of-3 or final chair adjudication of the EAEC)	nominal	Yes No
data_ep_SAR	No report	pep_u_2of3chair_SAR 	Uncorrected primary EP (based on a 2-of-3 or final chair adjudication of the EAEC)	nominal	Yes No
data_ep_SAR	No report	date_pep_c_2of3chair_SAR 	Date of (corrected) primary EP (based on a 2-of-3 or final chair adjudication of the EAEC)	date	n.a.
data_ep_SAR	No report	date_pep_u_2of3chair_SAR 	Date of uncorrected primary EP (based on a 2-of-3 or final chair adjudication of the EAEC)	date	n.a.

For each triplet eaec\_adjudication variable, an unique composite variable will be generated based on a 2-of-3 or chairman decision. For better readability, the index (\*) is used instead of the index "2of3chair\_SAR", which is used for other derived data.

[figure not shown]
Data file: Identifier	Notes	Variable name	Variable label	Variable level	Nominal values
parent_record_id					
data_ep_SAR	No report	death_2of3chair_SAR 	All cause death (based on a 2-of-3 or final chair adjudication of the EAEC)	nominal	Yes / No
data_ep_SAR	No report	date_death_2of3chair_SAR 	Date of death (based on a 2-of-3 or final chair adjudication of the EAEC)	date	n.a.
data_ep_SAR	No report	cvdeath_2of3chair_SAR 	CV death (based on a 2-of-3 or final chair adjudication of the EAEC)	nominal	Yes / No
data_ep_SAR	No report	date_cvdeath_2of3chair_SAR 	Date of HTX (based on a 2-of-3 or final chair adjudication of the EAEC)	date	n.a.
data_ep_SAR	No report	htx_2of3chair_SAR 	HTX (based on a 2-of-3 or final chair adjudication of the EAEC)	nominal	Yes / No
data_ep_SAR	No report	date_htx_2of3chair_SAR 	Date of HTX (based on a 2-of-3 or final chair adjudication of the EAEC)	date	n.a.

Data file: Identifier	Notes	Variable name	Variable label	Variable level	Nominal values
parent_record_id data_ep_SAR	No report	hf_2of3chair_SAR 	Hospitalization or urgent visit for worsening of the patient status due to heart failure, or death due to heart failure (based on a 2-of-3 or final chair adjudication of the EAEC)	nominal	Yes / No
data_ep_SAR	No report	date_hf_2of3chair_SAR 	Date of hospitalization or urgent visit for worsening of the patient status due to heart failure, or death due to heart failure (based on a 2-of-3 or final chair adjudication of the EAEC)	date	n.a.
data_ep_SAR	No report	arr_2of3chair_SAR 	hospitalization resulting from an arrhythmia or death resulting from arrhythmia (based on a 2-of-3 or final chair adjudication of the EAEC)	nominal	Yes / No
data_ep_SAR	No report	date_arr_2of3chair_SAR 	Date of hospitalization resulting from an arrhythmia or death resulting from arrhythmia (based on a 2-of-3 or final chair adjudication of the EAEC)	date	n.a.

Data file: Identifier parent_record_id	Notes	Variable name	Variable label	Variable level	Nominal values
data_ep_SAR	No report	acs_2of3chair_SAR 	Hospitalization resulting from acute coronary syndrome or death resulting from acute coronary syndrome. (based on a 2-of-3 or final chair adjudication of the EAEC)	nominal	Yes / No
data_ep_SAR	No report	date_acs_2of3chair_SAR 	Date of hospitalization resulting from acute coronary syndrome or death resulting from acute coronary syndrome (based on a 2-of-3 or final chair adjudication of the EAEC)	date	n.a.
data_ep_SAR	No report	stroke_2of3chair_SAR 	Hospitalization resulting from stroke (based on a 2-of-3 or final chair adjudication of the EAEC)	nominal	Yes / No
data_ep_SAR	No report	date_stroke_2of3chair_SAR 	Date of hospitalization resulting from stroke (based on a 2-of-3 or final chair adjudication of the EAEC)	date	n.a.

Data file: Identifier parent_record_id	Notes	Variable name	Variable label	Variable level	Nominal values
data_ep_SAR	No report	bleed_2of3chair_SAR 	hospitalization resulting from major bleeding or death resulting from major bleeding (based on a 2-of-3 or final chair adjudication of the EAEC)	nominal	Yes / No
data_ep_SAR	No report	date_bleed_2of3chair_SAR 	Date of hospitalization resulting from major bleeding or death resulting from major bleeding (based on a 2-of-3 or final chair adjudication of the EAEC)	date	n.a.
data_ep_SAR	No report	emb_2of3chair_SAR 	hospitalization resulting from systemic embolism or death resulting from systemic embolism (based on a 2-of-3 or final chair adjudication of the EAEC)	nominal	Yes / No
data_ep_SAR	No report	date_emb_2of3chair_SAR 	Date of hospitalization resulting from systemic embolism or death resulting from systemic embolism (based on a 2-of-3 or final chair adjudication of the EAEC)	date	n.a.

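### The new Undetermined value for hospitalisations and urgent visits is missing from the two cause variables behind the corrected primary endpoint

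*SAP*

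**What the plan says.** SAP chapter 10 describes a two-step adjudication. The EAEC first classifies each event with all available information. Then, "for any possible endpoint, the most probably adjudication result without BioMonitor information is documented". The corrected result drives the analysis: "The analyses of the endpoints will be based on this variables type\_of\_event\_ae2 and death\_prim\_cause2". The uncorrected variables serve an additional analysis of the primary endpoint.

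The variable tables in the same chapter give the permitted values:

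- `type_of_event_ae` (uncorrected cause of admission or urgent visit) has eleven values, the last three being "other cardio-vascular non-cardiovascular Undetermined hospitalization or undetermined urgent visit". Footnote 46, attached to this variable only, marks the Undetermined value as new.
- `type_of_event_ae2`, labelled "The most probably adjudication result without BioMonitor information would have been", has ten values and stops at `non-cardiovascular`.
- `type_of_event_ae_c`, whose label begins "Primary cause of Unscheduled hospitalisation / urgent visit (corrected data", has the same ten.
- The death variables `death_prim_cause`, `death_prim_cause2` and `death_prim_cause_c` (the last labelled "Primary cause of death (corrected data") all include `undetermined`.

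The MACE definition quoted in the same chapter does not name undetermined hospitalisations.

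**The concern.** Footnote 45 gives the purpose of the corrected variables: device information exists in one arm only, so the primary analysis uses the adjudication made as if that information were absent. This works only if the EAEC has the same answers available in both steps. For admissions and urgent visits it does not. An adjudicator who believes that an event would have been unclassifiable without the device cannot record that and must choose one of ten other values. Some of these are MACE components, such as heart failure or arrhythmia; others are not.

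Because all death-cause lists carry `undetermined`, the gap looks like an incomplete update and not a deliberate choice. At stake is whether the same clinical picture can count differently in the two arms of the primary analysis. The cause-specific secondary endpoints rest on the same adjudication. SAP 11.6 also plans hazard ratios under both adjudications if the primary alternative is accepted. With unequal lists, the difference between them would mix the effect of device information with the effect of list content.

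**Working it through.** **1. Lists compared value by value (SAP chapter 10).**

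| Variable | Number of values | Undetermined listed |
|---|---|---|
| `type_of_event_ae` | 11 | yes |
| `type_of_event_ae2` | 10 | no |
| `type_of_event_ae_c` | 10 | no |
| three death-cause variables | same list in each | yes |

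The Undetermined value is the only difference among the first three rows. Two of the ten remaining values, `other cardio-vascular` and `non-cardiovascular`, are residual categories outside the MACE list.

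**2. What follows under each plausible derivation of `type_of_event_ae_c`.** The rule is in footnote 47, and the rules for the endpoint flags `pep_c` and `pep_u` are in footnotes 49 and 50. Their text is not available here, and this is not counted against the plan.

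- *If `type_of_event_ae_c` takes `type_of_event_ae2` for every event:* an event coded Undetermined in either arm has no listed corrected value. Both arms meet the gap.
- *If it takes `type_of_event_ae2` only when `contribution_significant` = Yes and otherwise copies `type_of_event_ae`:* unflagged events can carry Undetermined, so the printed list for `type_of_event_ae_c` is incomplete. Flagged events are then the only ones denied the value. They need device data, so they lie essentially in the BioMonitor arm.

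The printed lists need correcting under both rules. Only the second makes the gap one-sided.

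**3. The plan's event number.** Inputs are HR 0.7452, 80% power and 372 events (protocol 11.2 and 11.3), one-sided alpha 0.025 and 1:1 allocation.

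- Schoenfeld: 4 × (1.960 + 0.842)² / (ln 0.7452)² gives 363.
- Freedman: (1.960 + 0.842)² × (1.7452 / 0.2548)² gives 369.
- Schoenfeld with the three-stage O'Brien-Fleming inflation factor 1.0174 gives 369.3.

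All are within 3% of 372, so the planned figure reproduces and is not in dispute.

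**4. Possible size, on assumed counts.** The documents give neither the number of undetermined events nor the number flagged. Suppose that k BioMonitor-arm admissions are coded to a MACE cause, each is the patient's first MACE, and Undetermined would not have been MACE. With D events split in the ratio HR : 1, the BioMonitor arm has D × 0.7452 / 1.7452 events. At D = 372 this is 158.8 against 213.2; at D = 248 it is 105.9 against 142.1. The apparent HR is (BioMonitor events + k) / control events. Power is Φ(√((D + k)/4) × |ln HR| − z) at one-sided alpha 0.02476. The value 248 is the formerly planned second interim count (SAP 5.8). It serves as a lower total because protocol 11.2 says that the intended number may not be reached.

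| k | HR, D = 372 | Power | HR, D = 248 | Power |
|---|---|---|---|---|
| 0 | 0.745 | 0.81 | 0.745 | 0.64 |
| 2 | 0.755 | 0.78 | 0.759 | 0.58 |
| 5 | 0.769 | 0.72 | 0.780 | 0.50 |
| 10 | 0.792 | 0.62 | 0.816 | 0.37 |

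If the same admissions go to a residual non-MACE value and Undetermined is also non-MACE, the primary endpoint does not change for any k.

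**The case against.** The strongest reply is that an unclear event already has somewhere to go. Example 2 in the SAP change history (Version 2.0) describes an admission for general malaise that only the device explains, and assumes that without the device it would be classed as other cardiovascular, a non-MACE value. The field also asks for the most probable result, which is a best judgement by design, and none of the three examples there ends in an undetermined cause. This stands as far as it goes: it makes a nil effect plausible. It does not settle the matter. The example appears under Version 2.0 and the Undetermined value is described as new, so the example may predate it. Nothing printed directs unclear events to a non-MACE value.

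A reader might infer that BioMonitor-arm events alone are forced into a definite cause. The documents do not support this. Chapter 10 does not restrict the second adjudication by arm, the one-sided version needs a derivation rule that cannot be read here, and two of the ten values are residual.

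A reader might also infer that every corrected variable is affected. The corrected death causes do hold `undetermined`.

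Finally, the shift shown in the working moves the hazard ratio towards 1. In that scenario the cost is power and not a false claim of benefit, and the analysis on uncorrected variables uses the full list. Both points are fair and limit the seriousness.

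**Conclusion.** The mismatch is real and confined to the cause of hospitalisations and urgent visits: eleven values without the correction, ten with it. It sits in variables that feed the confirmatory analysis and runs against the stated purpose of the correction. Differential classification between arms is possible but not demonstrated, and its size is unknown. It is nil if such events are coded to a non-MACE value and Undetermined is itself non-MACE. The tabulated shifts (HR 0.755 to 0.792 at 372 events for two to ten extra events) rest wholly on assumed counts and on every such event becoming a first MACE.

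It would go too far to conclude that the primary result is biased. The supportable conclusion is that a value list and a counting rule are incomplete as printed and should be settled in writing before lock. That matters more than usual because SAP 1.4 states that all persons responsible for this SAP version were unblinded, so the choice should not be left to programming.

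**What to change.** 1. Add the Undetermined value to `type_of_event_ae2` and `type_of_event_ae_c`, in the database and in SAP chapter 10.
2. State whether an undetermined hospitalisation or urgent visit counts as MACE, with the same answer in `pep_c` and `pep_u` and in both arms.
3. Before database lock, have the EAEC, blinded to results, re-confirm `type_of_event_ae2` against the full list. Apply one rule to every event whose coding could be affected: those with `contribution_significant` = Yes and those coded Undetermined in `type_of_event_ae`. Re-opening only the device-flagged events would be a one-sided review with its own risk of bias.

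The cost is one list value, one sentence in the SAP and a small amount of EAEC re-review. The number of events to re-review is not given in the documents.

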#### 7.1.3.7 Major bleeding requiring hospitalization

The occurrence of major bleeding requiring hospitalization will be recorded and analyzed.

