#### 8.3.3.7 Time to first hospitalization resulting from major bleeding

Assessment of the time from randomization to the first hospitalization resulting from major bleeding or death resulting from major bleeding. A specified endpoint definition will be given by the members of the EAEC and documented in the charter agreement.

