### 19.2. Variables

#### *CIP Chapter 8.3.3.7 Time to first hospitalization resulting from major bleeding*

*Assessment of the time from randomization to the first hospitalization resulting from major bleeding or death resulting from major bleeding. A specified endpoint definition will be given by the members of the EAEC and documented in the charter agreement.*

Data file: Identifier patient_ display_id_full	Notes	Variable name	Variable label	Variable level	Nominal values
data_SAR	descr.	any_bleed_ITT_SAR 	Any hospitalization resulting from major bleeding or death resulting from major bleeding after effective randomization ITT	nominal	Yes / No
data_SAR	No report	date_1bleed_ITT_SAR 	Date of 1st hospitalization resulting from major bleeding or death resulting from major bleeding after effective randomization ITT	date	n.a.
data_SAR	descr.	days_effrand_to_1bleed_ITT_SAR 	Days from effective randomization to 1st hospitalization resulting from major bleeding or death resulting from major bleeding or termination ITT	scale	n.a.

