### 22.2. Variables

*CIP Chapter 8.3.3.10 Type of initiated therapies.*

*Evaluation of the diagnoses and consequent type of therapies based on ICM-detected arrhythmias.*

Data file: Identifier parent_record_id (related to the AE record ID)	Notes	Variable name	Variable label	Variable level	Nominal values
internal_adjudication	descriptive * #	adj_rhythm_multi	Rhythm	nominal	Atrial fibrillation Atrial flutter AV block Bradycardia frequent VPBs non-sustained VT sustained VT polymorphic VT/VF Other SVT Pause None
internal_adjudication	descriptive *	adj_drug	Drug	nominal	Antiarrhythmic BB Diuretic OAC Other None
internal_adjudication	Case listing	adj_drug_txt	Drug text	text	n.a.
internal_adjudication	descriptive #	adj_device	Device	nominal	Ablation Cardioversion ICD Other PM None
internal_adjudication	Case listing	adj_device_txt	Device text	text	n.a.

\*2x3 contingency table; # 2x3 contingency table

 analysis\_set\_itt\_SAR = Yes

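### The bleeding endpoint counts death from major bleeding, but the EAEC cause-of-death list has no value for a fatal non-cardiovascular bleed

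*SAP*

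**What the plan says.** Protocol 8.3.3.7 defines the endpoint as "Assessment of the time from randomization to the first hospitalization resulting from major bleeding or death resulting from major bleeding". SAP 19.2 carries this into the patient-level variable: "Any hospitalization resulting from major bleeding or death resulting from major bleeding after effective randomization ITT". The event-level variable that feeds it, `bleed_2of3chair_SAR` in SAP 10, is labelled "hospitalization resulting from major bleeding or death resulting from major bleeding (based on a 2-of-3 or final chair adjudication of the EAEC". None of these limits the bleed by site.

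The EAEC records causes on two kinds of list, both in SAP 10. The list for unscheduled hospitalizations and urgent visits (`type_of_event_ae`) includes "Stroke Major bleeding Transient ischemic attack Systemic embolism other cardio-vascular non-cardiovascular Undetermined hospitalization or undetermined urgent visit", so major bleeding is a value there without any cardiovascular qualifier. The list for deaths reads "Myocardial infarction Heart failure Sudden cardiac death Stroke Cardiovascular hemorrhage Systemic embolism other cardio-vascular non-cardiovascular undetermined". The same nine death values are given for the uncorrected variable (`death_prim_cause`), for the adjudication without BioMonitor information (`death_prim_cause2`) and for the corrected variable (`death_prim_cause_c`). Death without prior hospitalization is a separate type of event in the same section.

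The matching objective, Protocol 7.1.3.7, is narrower than the endpoint: "The occurrence of major bleeding requiring hospitalization will be recorded and analyzed".

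**The concern.** The endpoint has a fatal part, but the form on which deaths are classified has no value that matches it. A fatal gastrointestinal bleed at home is the plain example. Read at face value, 'Cardiovascular hemorrhage' does not describe it, and the next fitting value is 'non-cardiovascular', which it would share with a cancer death.

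Bleeding is not a peripheral outcome here. Patients on permanent oral anticoagulation for atrial fibrillation are excluded at entry (Protocol 8.9.3), and the drug categories that SAP 22.2 uses after detected arrhythmias are "Antiarrhythmic BB Diuretic OAC Other None". If monitoring leads to more anticoagulation, major bleeding is the harm that one would want counted completely, fatal cases included.

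**Working it through.** **Inputs.** Endpoint wording: Protocol 8.3.3.3 to 8.3.3.8 and SAP 19.2. Code lists and derived variables: SAP 10. MACE definition: Protocol 8.3.1. The rule for `bleed_2of3chair_SAR` sits in SAP footnote 67, which was not legible in the text available for this review. The scenarios below therefore assume that 'Cardiovascular hemorrhage' is the death value that feeds the bleeding endpoint.

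**Step 1: does each component with a fatal form have a death value?** The pairing is by ordinary meaning of the labels.

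| Component | Matching death value |
|---|---|
| Heart failure | Heart failure |
| Arrhythmia | Sudden cardiac death |
| Acute coronary syndrome | Myocardial infarction |
| Stroke | Stroke |
| Systemic embolism | Systemic embolism |
| Major bleeding | Cardiovascular hemorrhage only |

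Only the bleeding value is narrower than its endpoint.

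**Step 2: pass each kind of major bleed through the listed codes.**

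| Course and code | Bleeding endpoint | MACE |
|---|---|---|
| Acute unscheduled admission for major bleeding, survived | yes | yes |
| Same admission, then death coded 'non-cardiovascular' | yes, by the admission | yes, by the admission |
| Death before admission, 'Cardiovascular hemorrhage' | yes (assumed mapping) | yes |
| Death before admission, 'other cardio-vascular' | no | yes |
| Death before admission, 'undetermined' | not identifiable as bleeding | not stated in the legible text |
| Death before admission, 'non-cardiovascular' | no | no |

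**Step 3: could the unseen footnote rescue the last row?** The variable's label says that it rests on EAEC adjudication. For a death without prior hospitalization, the listed EAEC cause variable is the death code. A rule that took in every death coded 'non-cardiovascular' would also take in cancer deaths. So no sensible rule on the listed variables can pick out the bleeding deaths, whatever the footnote says.

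**Step 4: where does the MACE column come from?** From Protocol 8.3.1, not from the code list. MACE counts major bleeding only as an acute unscheduled hospitalization, and counts death only if cardiovascular. A new death code would not change that column.

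**Step 5: size.** The plan gives no figure for this point. The nearest is the 372 primary events of Protocol 11.2. With HR 0.7452, one-sided alpha 0.025, 80% power and 1:1 allocation:
- Schoenfeld: 4 × 2.8016² / 0.2941² = 363.
- Freedman: (1.7452 / 0.2548)² × 2.8016² = 369.
- Schoenfeld with an assumed group-sequential inflation of 1.016 to 1.02: 369 to 371.

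The 372 is thus reproduced to within about 2.4%.

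As an illustration only, suppose 40 to 60 major bleeds, of which 3% to 8% are fatal non-cardiovascular bleeds before admission. Neither range comes from the documents. That gives 3% × 40 = 1.2 to 8% × 60 = 4.8 deaths. As a bound on relevance to the primary test, treat such deaths as primary events lost from 372. Power is Φ(√d × 0.2941 / 2 − 1.964), using the final alpha of 0.02476 from Protocol 11.1.1.

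| Events lost | Power |
|---|---|
| 0 | 80.8% |
| 1 | 80.7% |
| 5 | 80.3% |
| 10 | 79.8% |
| 19 | 78.8% |

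**The case against.** The strongest objection is that the coding step is not settled by the SAP. Protocol 8.3.3.7 leaves the specific endpoint definition to the EAEC charter, and Protocol 8.3.1.1 and 9.8.1 leave the adjudication process and criteria to it as well. If the charter places every fatal major bleed under 'Cardiovascular hemorrhage', such a death would count for bleeding and for MACE, and no event would be missed. This stands as a limit, and it makes the point conditional. It does not remove the need for a statement in the SAP: under that convention, bleeds that are not cardiovascular in the ordinary sense would count as cardiovascular deaths.

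A second objection is that the information is not lost. Protocol 8.9.4.2 requires a death certificate or report with primary cause for every death, and the EAEC adjudicates all deaths. That is correct. The gap is in the coded variables from which the endpoint is derived, and this is why it is cheap to close.

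A third is that objective 7.1.3.7 speaks only of bleeding that requires hospitalization, so out-of-hospital deaths may never have been meant. But the endpoint section and both SAP variable labels name death, and they govern the analysis.

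A reader might go further and infer that the plan treats the worst bleeding outcome as no event, or that the MACE comparison is flawed because a survived admitted bleed counts and a fatal one at home does not. The documents do not support either reading. The death counts in the all-cause death endpoint (Protocol 8.3.3.1, SAP 13), a bleed that reaches hospital and then proves fatal counts through the admission, and the composition of MACE is prespecified. Nor do the documents show that the gap favours the BioMonitor arm: they give no anticoagulation rate by arm.

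**Conclusion.** The point holds as a mismatch between a secondary endpoint and the form that feeds it. If the EAEC applies the death labels in their ordinary sense, a fatal non-cardiovascular bleed without prior hospitalization cannot enter the bleeding endpoint that by definition includes it, and appears only in all-cause death. This rests on two things: the ordinary reading of 'Cardiovascular hemorrhage', since the charter is not available, and derivation from the listed EAEC variables alone.

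The number of such deaths is not in the documents and is likely small; the range of about 1 to 5 above rests wholly on assumptions. The effect on the primary result is negligible. Protocol 8.3.3 already says that the component endpoints are not powered for confirmatory testing. What is at stake is the completeness of one secondary harm endpoint. This is a low-severity, inexpensive improvement.

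**What to change.** Add to SAP 10 and the EAEC form a yes/no item, 'death resulting from major bleeding'. Splitting 'non-cardiovascular' into hemorrhage and other is an alternative form of the item.

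Have the EAEC, blinded to arm, complete it before database lock for every death not already coded 'Cardiovascular hemorrhage'. This must include deaths coded 'undetermined' and 'other cardio-vascular', since a re-read of the 'non-cardiovascular' deaths alone would leave bleeds in those two categories unfound.

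Derive `bleed_2of3chair_SAR` and its date from admissions coded 'Major bleeding' plus all deaths that are so flagged or coded 'Cardiovascular hemorrhage'. Put this mapping in writing before the re-read starts, because SAP 1.4 states that all those responsible for SAP 3.0 were unblinded. Leave the MACE definition unchanged.

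The cost is one form item and a short additional adjudication task for the existing committee, on death reports that the protocol already requires. No new patient data are needed.
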